1.2.2 Secondary Objectives

- To assess haemolysis occurrence based on blood collection device, catheter device configuration.
- To evaluate blood draw fill time
- To determine the relationship, if any, between catheter blood draw patency indwell time and presence of intra/extravenous thrombi, catheter angle/tip location *in situ*, catheter length in vessel, vein depth from skin surface, C/V ratio, and vessel anatomy
- To evaluate changes in vessel dimensions, PIVC position (insertion angle and *in situ* tip position), and hemodynamics from baseline throughout indwell time

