2.1 Study Design

This is a single-center, open-label, multi-visit, self-controlled study design, in 40 healthy participants, randomized by gauge of peripheral intravenous catheter (PIVC) device into the lower arm cephalic vein of both arms. The purpose of this feasibility study is to assess impact of catheter length and gauge on PIVC indwell time over a multi-day (72 hour) period. This study will also evaluate the incidence of haemolysis from PIVC using a LLAD and vacutainer tube (2mL, 6mL) blood collection method compared to venipuncture from the antecubital fossa.

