2.6 Preliminary Analysis

In order to answer critically urgent business questions, a preliminary analysis will be performed by an independent statistician prior to the final database lock. This analysis will be limited to the analysis of the following specific endpoints:

- Indwell time (as described in section 5.2.1.1) and ranking of factor influencing indwell time (as described in section 5.2.2.3 by item 7)
- Haemolysis as a continuous measurement by device configuration and over time, including baseline venipuncture rate as relative comparator, as described in section 5.2.2.1 by item 1 (including the preliminary Boruta analysis)
- Rate of occurrence of Haemolysis by device configuration and over time, including baseline venipuncture rate as relative comparator, as described in section 5.2.2.1 by item 2 (including the preliminary Boruta analysis)
- Thrombus observation by device configuration over time, as described in section 5.2.2.3 by items 1, 2, 3, 4 and 7
- Incidence of failure modes for device removal, as described in section 5.2.1.2

The results of the preliminary analysis will be communicated by the independent statistician to [name] (Associate Director - Biomedical Engineering) who will be responsible for sharing them with [name] (Director - Product Development Engineering), select MDS designees, and [name] (Director/Principal Scientist - Parenteral Research). Preliminary analysis will not be shared beyond those required for making time-critical business decisions on behalf of the MDS business unit.

Every GCD employee involved in the study execution, especially the lead study statistician, as well as all site employees involved in the study execution, will remain blinded to the results of this preliminary analysis until database lock.

It is understood by all parties that the results of this primary analysis will be subject to confirmation after database lock and fulfillment of all the processes related to data quality described in the Data Management Plan.

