2.7 Study Procedure

The time-windows for collection of the primary, secondary and exploratory endpoints are detailed in Table 2.7.1.

The primary endpoint data (catheter dwell time) and exploratory endpoint data (PIVC complications) will be collected over 7 time-windows (see text highlighted in orange on Table 2.7.1). The secondary endpoint data (cfHb, blood draw time) will be collected over 8 discrete timepoints (including baseline, see text highlighted in red on Table 2.7.1).

All other secondary endpoint data (e.g., blood flow velocity, vessel diameter), except incidence of extravenous thrombus (assessed once the catheter is removed), will be collected over 15 timepoints (see text

highlighted in blue and grey on Table 2.7.1). Please note that the cells that indicate ‘Day’ in Table 1 are indicating the interventional visit days and are not inclusive of the screening visit or follow-up visit.

The flush pressure profile exploratory endpoint data will be collected over 7 timepoints (see text highlighted in blue on Table 2.7.1).

Table 2.7.1: List of sampling time points for primary, secondary, and exploratory endpoints. cfHb: cell-free hemoglobin; TIP: catheter tip position; BFV: blood flow velocity; C/V: catheter to vein ratio; PRES: in vivo pressure; PIVC: peripheral intravenous catheter; FILL: blood draw fill time. Time T+00:00 is the time of insertion

Day	Visit	Timepoint code	Approximate (hh:mm)	Time	Measurements taken
Day 1	Baseline	D1.1	T-00:60		TIP, BFV, C/V via ultrasound (no indwelling catheter)
		D1.2	T-00:40		cfHb via venipuncture
	Morning	D1.3	T+00:15		TIP, BFV, C/V via ultrasound, PRES via PIVC during flush
		D1.4	T+00:25		cfHb, FILL via PIVC
	Afternoon	D1.5	T+00:35		TIP, BFV, C/V via ultrasound
		D1.6	T+06:00		TIP, BFV, C/V via ultrasound, PRES via PIVC during flush
		D1.7	T+06:15		cfHb, FILL via PIVC
		D1.8	T+06:25		TIP, BFV, C/V via ultrasound
Day 2	Morning	D2.1	T+24:00		TIP, BFV, C/V via ultrasound, PRES via PIVC during flush
		D2.2	T+24:15		cfHb, FILL via PIVC
	Afternoon	D2.3	T+24:25		TIP, BFV, C/V via ultrasound
		D2.4	T+30:00		TIP, BFV, C/V via ultrasound, PRES via PIVC during flush
		D2.5	T+30:15		cfHb, FILL via PIVC
		D2.6	T+30:25		TIP, BFV, C/V via ultrasound
Day 3	Morning	D3.1	T+48:00		TIP, BFV, C/V via ultrasound, PRES via PIVC during flush
		D3.2	T+48:15		cfHb, FILL via PIVC
	Afternoon	D3.3	T+48:25		TIP, BFV, C/V via ultrasound
		D3.4	T+54:00		TIP, BFV, C/V via ultrasound, PRES via PIVC during flush

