5.2.2 Statistical Analysis of Secondary Endpoints

5.2.2.1 Haemolysis

It is hypothesized that:

- The cfHb concentrations observed in blood samples (all vacutainers, at all timepoints) collected from shorter catheters will be greater than that observed in longer catheters.

- The cfHb observed in blood samples (all vacutainers, at all timepoints) collected from catheters with a larger gauge (smaller bore) will be greater than blood collected from smaller gauge (greater bore).
- The cfHb observed in blood samples (all catheters) collected into greater volume vacutainers will be greater than blood collected into smaller volume vacutainers.

Haemolysis will be assessed through:

1. Quantification of average cfHb concentrations measured at each time point listed in red in Table 2.7.1. A linear mixed effect model will be used with cfHb as response and subject as random effect. Time, gauge, length, vacutainer volume and baseline (at D1.2) cfHb (2ml, 6ml measures will be used as separate continuous variables and will be retained in the model if significant) will be fixed effects. An example of the summary statistics table and associated graphical representation are provided in Appendix A by Table A.10.2 and in Appendix B by Figure B.3.1, respectively.
2. Rate of occurrence measured using the results of the cfHb concentrations at each time point listed in red in Table 2.7.1. Samples will be considered positive for haemolysis for cfHb concentration $\geq 50\text{mg/dL}$ ¹. A logistic mixed effect model will be used with haemolysis occurrence as response and subject as random effect. Time, gauge, length, vacutainer volume and baseline (at D1.2) cfHb will be fixed effects. Tables summarizing occurrence rates per device per time point and associated graphical representation will be similar to the one provided for rate of occurrence measured using the results of the AU480 analysis (see next item) in Appendix A by Table A.10.2 and in Appendix B by Figures B.4.1 and B.4.2, respectively. Contrast based multiple comparisons will be used to compare haemolysis rate between conditions (between gauge, between length) at each timepoint.

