3. Rate of occurrence measured using the results of the AU480 Analysis at each time point listed in red in Table 2.7.1. Samples will be considered positive for haemolysis for AU480 output of + (50-99mg/dL), ++ (100-199mg/dL), +++ (200-299mg/dL), ++++ (300-500mg/dL) and +++++ (>500mg/dL), i.e. anything different from N (<50mg/dL)². A logistic mixed effect model will be used with haemolysis occurrence as response and subject as random effect. Time, gauge, length, vacutainer volume and baseline (at D1.2) cfHb will be fixed effects. Examples of the table summarizing occurrence rates per device per time point and associated graphical representation are provided in Appendix A by Table A.10.2 and in Appendix B by Figures B.4.1 and B.4.2, respectively. Contrast based multiple comparisons will be used to compare haemolysis rate between conditions (between gauge, between length) at each timepoint.
4. Rate of occurrence measured using the results of the visual assessment at each time point listed in red in Table 2.7.1. Samples will be considered positive for haemolysis for visual values $\geq 50\text{mg/dL}$, as shown on the reference chart. A logistic mixed effect model will be used with visually observed haemolysis occurrence as response and subject as random effect. Time, gauge, length, Vacutainer tube volume and baseline (at D1.2) cfHb will be fixed effects. An example of the table summarizing occurrence rates per device per time point is provided in Appendix A by Table A.10.2. Graphical representation will be similar to the ones given as example for the AU480 analysis. Contrast based multiple comparisons will be used to compare haemolysis rate between conditions (between gauge, between length) at each timepoint.

In each case, i.e. for cfHb, AU480 and visual assessment, modeling will be preceded by an assessment of the importance of potential covariates using the Boruta algorithm. The covariates of interest will include,

¹A separate assessment of the relationship between the cfHb and AU480 measurements will be performed in order to check the validity of this threshold, which could be modified upon review of these results.

²A separate assessment of the relationship between the cfHb and AU480 measurements will be performed in order to check the validity of this threshold, which could be modified upon review of these results.

but will not be limited to:

- Presence of thrombus
- Size of thrombus
- Proximity of thrombus to tip of catheter
- Draw rate

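### The SAP names venipuncture as the comparator for haemolysis but specifies no PIVC-versus-venipuncture contrast, and leaves unclear whether the D1.2 sample is a covariate, a response or both

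*SAP*

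**What the plan says.** SAP 2.1 states the second purpose of the study: "This study will also evaluate the incidence of haemolysis from PIVC using a LLAD and vacutainer tube (2mL, 6mL) blood collection method compared to venipuncture". The protocol synopsis says the same. The first secondary objective (SAP 1.2.2; protocol 3.1) is "To assess haemolysis occurrence based on blood collection device, catheter device configuration", so collection device is named alongside catheter configuration.

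SAP 5.2.2.1 sets out four analyses:

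- **Item 1, cfHb as a continuous response.** A linear mixed model with participant as random effect and these fixed effects: "Time, gauge, length, vacutainer volume and baseline (at D1.2) cfHb (2ml, 6ml measures will be used as separate continuous variables". The baseline terms stay only if significant.
- **Items 2-4, occurrence by cfHb at or above 50 mg/dL, by AU480 and by visual reading.** Logistic mixed models. Items 2 and 3 state "Time, gauge, length, vacutainer volume and baseline (at D1.2) cfHb will be fixed effects", and item 4 says nearly the same. For each of the three, "Contrast based multiple comparisons will be used to compare haemolysis rate between conditions (between gauge, between length) at each timepoint".

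Two other places bear on the role of the venipuncture sample. SAP 2.6 asks for a preliminary analysis of haemolysis "including baseline venipuncture rate as relative comparator, as described in section 5.2.2.1 by item 1", with a matching line for the occurrence rate that points to item 2. SAP 2.7 says cfHb and blood draw time "will be collected over 8 discrete timepoints (including baseline, see text highlighted in red on Table 2.7.1", and items 1-4 take their measurements at the red time points.

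In the mock outputs, venipuncture results appear by gauge group in Table A.3.2. PIVC results appear by device and tube in Table A.8.1, at 0 to 72 hours, with no venipuncture column.

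**The concern.** A stated purpose and a secondary objective need a PIVC-minus-venipuncture estimate, and no analysis is defined that produces one. An analyst who follows 5.2.2.1 reports gauge, length, tube-volume and time effects, and leaves the collection-method question to a reader comparing two tables by eye. That discards the pairing: both samples come from the same person, nominally 65 minutes apart (T-00:40 and T+00:25 in Table 2.7.1).

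The gap matters most for the preliminary analysis in SAP 2.6. It asks for venipuncture as comparator to inform urgent decisions and refers to a section with no method for it. Whoever runs that analysis must choose the time point, tube volume and estimator without guidance.

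**Working it through.** **1. The plan's own figure.** The only power figure is 0.8054, for the logrank test on indwell time (SAP 2.4: 19 and 20 participants, medians 1 and 3 days, 3 days of follow-up, two-sided 0.05). Expected events are 19 × (1 − 0.5³) + 20 × (1 − 0.5) = 16.6 + 10 = 26.6. Power is then 0.809 by Schoenfeld's formula and 0.806 by a Lakatos-type calculation, so the figure reproduces. It has no bearing on haemolysis, for which no precision or power is stated.

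**2. Does any reported term carry the contrast?** If D1.2 is only a covariate, every response row is a PIVC sample. Adding a constant to all PIVC results then changes only the intercept. I confirmed this on simulated data with the item 1 structure (40 participants, two catheters each, seven draws, two tubes). Raising every PIVC value by 30 mg/dL moved the intercept by 30 and the time, gauge, length, volume and baseline coefficients by 0. No reported effect or planned contrast would show a collection-method difference of any size.

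**3. Could D1.2 be a response?** SAP 2.7 permits that reading: eight red time points are D1.2 plus seven PIVC draws. Against it:

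- Venipuncture has no catheter length, and its needle is 21G (protocol 7.1), neither 20G nor 22G. Length and gauge as catheter attributes are therefore undefined for those rows, and SAP 5.2.5 does not impute.
- D1.2 cfHb would be on both sides of the same model.
- Table A.8.1 has response rows only at 0-72 hours, and Listing C.0.6 carries baseline cfHb as a column.
- The contrasts named for occurrence would still be gauge and length only.

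**4. Precision if the contrast is added.** Each configuration is placed in 20 participants (protocol 4.1). Pooling over gauge at one length gives 40. The documents give no discordance rate, so I assume 10-30%. With q the discordant proportion and the true difference near zero, half-width ≈ 1.96 × √(q/n):

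| q | n = 20 | n = 40 |
|---|---|---|
| 10% | 1.96 × √(0.10/20) = 13.9 points | 9.8 points |
| 20% | 1.96 × √(0.20/20) = 19.6 points | 13.9 points |
| 30% | 1.96 × √(0.30/20) = 24.0 points | 17.0 points |

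A paired difference d cannot exceed q, and the fuller variance is (q − d²)/n. For scale only, protocol 2.1 cites 3.3% for routine samples, 13.9% for 20G and 25.5% for 22G. Treating 3.3% as a venipuncture rate is an assumption. The gaps are 10.6 and 22.2 points, so q = 10% fits neither and q = 20% does not fit the second. With q = 30% and d = 22.2 points, the half-width at n = 20 is 1.96 × √((0.30 − 0.049)/20) ≈ 22 points.

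Under those same rates, and with independent outcomes within a person, exact McNemar power is about 3% (20G, n = 20), 27% (22G, n = 20) and 51% (average rate 19.7%, n = 40).

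For continuous cfHb the half-width is 1.96/√n within-person SDs of the difference: 0.44 SD at n = 20 and 0.31 SD at n = 40. No real SD is available, because the SAP tables hold dummy data.

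**The case against.** The best defence is that the SAP does not ignore the comparison. Section 2.6 names venipuncture as relative comparator for both continuous and binary haemolysis. Section 2.7 puts baseline among the red time points, so a time contrast against D1.2 could be read as PIVC versus venipuncture. Section 5.2.4 requires 95% CIs for means and percentages, so each method gets its own summary with an interval. This is also a feasibility study with no acceptance criteria, and no hypothesis in protocol 3.2.2 or SAP 5.2.2.1 concerns venipuncture.

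Much of this stands. A reader might infer that the SAP uses venipuncture everywhere as a covariate and nothing else, so that the contrast is ruled out. Sections 2.6 and 2.7 do not support that: the intention is visible and the role of D1.2 is ambiguous. Nor does each model adjust for its own venipuncture result. The AU480 and visual models adjust for baseline cfHb.

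The defence does not supply a method. Section 2.6 refers to items that define no comparison, the reading of D1.2 as a response fails for the reasons in step 3, and separate marginal intervals do not give an interval for the paired difference.

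**Conclusion.** The point holds as an unspecified contrast together with an inconsistency between SAP 2.6, 2.7 and 5.2.2.1. The plan as written yields no within-person estimate or interval for a stated purpose of the study, and it should be corrected.

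A reader might also infer that 40 pairs would settle the matter to within 10-17 points. That applies only to contrasts pooled over gauge. For a single configuration the figure is about 14-24 points, under the assumed 10-30% discordance and a difference near zero. The published rates in the protocol are background and are not stated as target differences. The added result should therefore be read as an estimate with a wide interval. That suits SAP 5.2, which gives estimation and significance similar weight.

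**What to change.** Add to SAP 5.2.2.1 a within-participant comparison of each PIVC configuration at D1.4 with venipuncture at D1.2, at the same tube volume:

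- For cfHb, report the mean paired difference with 95% CI.
- For cfHb at or above 50 mg/dL, AU480 and visual assessment, report the paired difference in proportions with 95% CI, using the venipuncture AU480 and visual results that currently enter no model.
- A mixed model with collection method as a factor (venipuncture and the four configurations) is an option if it converges. With 20 participants per configuration and possibly few events, the simple paired analysis is the safer default.
- Do not use D1.2 as both response and covariate in one model. Keep the existing baseline-adjusted models for gauge and length.
- Align 2.6 and 2.7 with 5.2.2.1: point 2.6 to the new item and state in 2.7 what role D1.2 has in each analysis.
- State that collection method cannot be separated from sampling site, sequence and needle.

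The cost is SAP wording and one additional analysis on samples already scheduled. The drawback is another set of wide intervals, which should be labelled as estimation.

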- Screening Blood Testing (as provided by Blood Testing CRF)
 - Coagulation Panel: PT & aPTT
 - Platelet Aggregometry: ADP, TRAP & Collagen Induced Maximal Amplitude
 - Blood Screening: Blood Glucose & Triglycerides
 - Liver Panel: ALT Average Measurement & AST Average Measurement

The significance of the most important features will be assessed by inclusion in the corresponding models and only significant covariates will be retained in the final model.

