5.2.2.2 Blood draw fill time

It is hypothesized that:

- The blood draw duration observed for blood samples (all vacutainers, at all timepoints) collected from shorter catheters will be decreased when compared to longer catheters of the same gauge.
- The blood draw duration observed for blood samples (all vacutainers, at all timepoints) collected from smaller gauge (larger bore) catheters will be decreased when compared to larger gauge (smaller bore) catheters of the same length, over time.
- The blood draw duration observed for blood samples (all catheters, at all timepoints) collected into greater volume vacutainers will be increased when compared to smaller volume vacutainers.

A linear mixed effect model will be used with blood draw fill time as response and subject as random effect. Time, device configuration (gauge, length and their interaction), Vacutainer tube volume and baseline (at D1.2) blood draw fill time will be fixed effects. Contrast based multiple comparisons will be used to compare blood draw fill time between conditions (between gauge, between length) at each timepoint. Example tables for summary statistics (overall and per time point for each Vacutainer tube volume are given in the Appendix section by Table A.9.1 and Table A.9.2, respectively. Graphical representations of distribution of blood draw time per device is provided in Figure B.5.1 and of average blood draw time is shown in the Appendix section by Figure B.5.3. Example tables for ANOVA tables (Table A.9.3) and multiple comparisons (Table A.9.4) can be found in the Appendix A

5.2.2.3 Relationship between catheter blood draw patency indwell time and presence of intra/extravenous thrombi, thrombus length, thrombus type catheter angle/tip location *in situ*, catheter length in vessel, vein depth from skin surface, C/V ratio, and vessel anatomy

Relationship, if any, will be assessed through the computation of:

1. Summary statistics stratified by indwell time considered as a discrete variable (0, 6, 24, 30, 48, 54, 72 hours)
2. Scatter plot showing time between initial Thrombus observation to time of removal per Device Configuration
3. Bar plot showing percentage of thrombus for each time point per device configuration
4. Scatter plot showing thrombus length as a function of time grouped by device configuration
5. Relationship between flush technique and presence of Thrombus

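### The haemolysis models can adjust gauge, length and tube-volume effects for draw rate and thrombus, both measured after insertion, so the coefficients may no longer be total device effects

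*SAP*

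**What the plan says.** The secondary objective in SAP 1.2.2 is "To assess haemolysis occurrence based on blood collection device, catheter device configuration". SAP 5.2.2.1 turns this into directional hypotheses. For length, cfHb in samples "collected from shorter catheters will be greater than that observed in longer catheters". For gauge, 22G is expected to give more cfHb than 20G. For tube volume, the larger tube is expected to give more than the smaller.

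The mixed models have subject as random effect. For the occurrence models based on cfHb and AU480, "Time, gauge, length, vacutainer volume and baseline (at D1.2) cfHb will be fixed effects". The continuous cfHb model and the visual-assessment model use the same set, with baseline cfHb entered separately by tube in the continuous one.

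A screening step then applies to cfHb, AU480 and visual assessment alike: "modeling will be preceded by an assessment of the importance of potential covariates using the Boruta algorithm". The candidates are thrombus presence, thrombus size, "Proximity of thrombus to tip of catheter", draw rate, and screening blood values. The leading features are entered in the corresponding models and "only significant covariates will be retained in the final model".

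SAP 5.2.4 adds two general rules. Models adjusted for significant effects are the ones used for analysis where possible, and non-significant variables are removed. Gauge and length are not exempted from removal.

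**The concern.** Draw rate and thrombus at the catheter arise after the device is in place. Randomisation supports the total effect of device choice on haemolysis. It does not support a coefficient that holds a post-insertion variable fixed. If gauge or length changes draw rate, and draw rate changes cfHb, then adjusting for draw rate takes that path out of the device coefficient. What remains answers a different question from the hypotheses in SAP 5.2.2.1.

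The removal rule adds to this. A gauge or length term that loses significance after the adjustment could be dropped from the model meant to test it.

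The result has a use. Protocol 4.1 says the trial informs whether product development continues, and SAP 2.6 sends the continuous and the rate-based haemolysis analyses, with their preliminary Boruta step, to an early readout for business decisions.

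**Working it through.** **Which candidates follow from the device?**

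- *Draw rate.* SAP 5.2.2.2 hypothesises that draw duration for samples "collected from shorter catheters will be decreased when compared to longer catheters of the same gauge", that 20G draws faster than 22G at the same length, and that the larger tube takes longer. Protocol 2.1 lists catheter length and gauge, and also suction and turbulence during the draw, among possible contributors to haemolysis, while calling the latter uncertain. The path from device through draw to haemolysis is therefore the plan's own reasoning. Draw rate itself is not defined in the SAP; here a shorter fill time for a given tube is read as a faster draw.
- *Thrombus.* Protocol 10.6 compares intravenous thrombus by length and gauge, and SAP 5.2.2.3 plots it by device configuration. Neither states a directional device effect. Protocol 4.2 points to participant variability in coagulation and platelet function, which could also drive it.

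**Direction.** The plan gives no haemolysis effect size, SD or power. Its only power figure, 0.8054 in SAP 2.4, belongs to indwell time and does not bear on this point. In a linear model, write T for the total device effect on cfHb, a for the device's shift in draw rate (in SDs), and b for the change in cfHb per SD of draw rate. Then:

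adjusted coefficient = T − a × b

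On the SAP's hypotheses T is positive for both the shorter catheter and 22G. But a is positive for the shorter catheter (faster draw) and negative for 22G (slower draw). One slope b therefore moves the two coefficients in opposite directions. If b > 0, the length effect shrinks and the gauge effect grows; if b < 0, the reverse. For tube volume the sign of a depends on how draw rate is defined.

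**Illustration; every effect size is an assumption.** T = 0.30 (shorter) and 0.50 (22G), in residual SDs; subject SD 0.5; residual SD 1. The layout follows the SAP: 40 participants × 2 lengths × 7 times × 2 tubes = 1,120 records, with 20 participants per gauge. There were 2,000 runs per scenario, with complete data and variance components taken as known. Each cell gives T − a × b, then the simulated mean coefficient with draw rate in the model. Power is without → with draw rate.

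| b | size of a | Shorter | Power | 22G | Power |
|---|---|---|---|---|---|
| 0 | 0.5 | 0.30; 0.299 | 99.9% → 99.8% | 0.50; 0.499 | 84.0% → 83.6% |
| 0.15 | 0.5 | 0.30 − 0.075 = 0.225; 0.225 | 100% → 95.0% | 0.50 + 0.075 = 0.575; 0.578 | 84.0% → 92.8% |
| 0.3 | 0.5 | 0.30 − 0.15 = 0.15; 0.150 | 99.7% → 68.8% | 0.50 + 0.15 = 0.65; 0.654 | 83.4% → 97.1% |
| 0.3 | 1 | 0.30 − 0.30 = 0; −0.005 | 99.8% → 4.6% | 0.50 + 0.30 = 0.80; 0.805 | 83.7% → 99.5% |
| −0.3 | 0.5 | 0.30 + 0.15 = 0.45; 0.448 | 99.6% → 100% | 0.50 − 0.15 = 0.35; 0.350 | 83.4% → 54.6% |

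Without draw rate, the models recovered about 0.30 and 0.50 throughout. Draw rate was significant at 0.05 in at least 99.8% of runs where b was not zero, and in about 5% where it was. The Boruta step was not simulated, so these are rates for the significance gate alone. The formula applies to the linear cfHb model; in the logistic models, adding a covariate also changes the scale of the odds ratio.

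**The case against.** Studying these covariates is legitimate. Protocol 2.1 names the mechanisms of thrombosis and haemolysis as an interest. Haemolysis is a secondary endpoint in a feasibility study with no acceptance criteria. A covariate must pass two gates: Boruta, which compares each feature with permuted shadow variables, and then significance in a model that already holds gauge and length. A mere proxy for the device would not reliably pass the second. Template Table A.8.1 also gives unadjusted cfHb means and haemolysis rates by configuration, tube and time.

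Most of this stands, and it limits the point. Adjustment is possible, not certain. The descriptive tables show the unadjusted picture but do not test the hypotheses. What the objection does not supply is a named model, free of post-insertion covariates, that answers the gauge, length and volume hypotheses.

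A reader might go further and infer that the device effect will be removed, or that a set share of it will be. The documents do not support this. The hypothesised directions imply inflation of one effect alongside shrinkage of the other. Assuming that 25%, 50% or 75% of an effect is mediated, and reporting that 0.75, 0.50 or 0.25 is left, only restates the assumption. A reader might also take thrombus to be an established consequence of gauge or length; no passage says so.

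**Conclusion.** The point holds as a gap in specification. Followed as written, the SAP can replace the total effects of gauge, length and tube volume on haemolysis with conditional ones, and can then drop a device term. This requires that draw rate or a thrombus variable affects haemolysis and is retained. The change to a conditional effect further requires that the device moves that variable. The plan hypothesises this last step for draw rate; for thrombus it is only plausible.

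Neither the size nor the net direction can be derived from the documents. In the tabulated scenarios with b positive, 25% to 100% of the length effect was lost while the gauge effect grew; with b negative, 30% of the gauge effect was lost while the length effect grew; with b zero there was no material harm. The matter should be settled before analysis, but it does not touch the primary endpoint.

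**What to change.** In SAP 5.2.2.1, name one pre-specified model per haemolysis measure as the test of gauge, length and tube volume. Allow only pre-insertion covariates in it: baseline cfHb, screening blood values, age, sex and BMI. Restrict the Boruta screen for that model to the same set. State that gauge, length and tube volume stay in whatever their p-values, as an exception to the removal rule in SAP 5.2.4.

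Report models that add draw rate or thrombus separately, as exploratory mechanism analyses. Define draw rate there, and do not present their gauge and length coefficients as device effects. Use the same split in the preliminary analysis of SAP 2.6.

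The cost is SAP wording and one extra model. No new data are needed and no planned analysis is lost.
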